3.2.2 Amgen Investigational Product Background: Erenumab

Erenumab is a human immunoglobulin G2 (IgG2) that is directed against the CGRP receptor complex and inhibits the action of CGRP.

Calcitonin gene-related peptide belongs to the calcitonin family of peptides and is expressed in both the central and peripheral nervous systems. It is prominently involved in the pathophysiology of migraine through nociceptive modulation, in the trigeminovascular system (Goadsby et al, 2002; Tajti et al, 1999). Nonclinical studies with erenumab demonstrated that it binds to and antagonizes both human and cynomolgus monkey CGRP receptors with high affinity and potency. Erenumab has been developed for the prevention of migraine in adults based on the observed long serum half-life in humans (28 days), clinical data demonstrating that small molecule CGRP receptor antagonists are effective in acute migraine reversal (Ho et al, 2008a; Ho et al, 2008b), prevention (Ho et al, 2014), and the strong rationale for CGRP's association with migraine pathophysiology (Goadsby et al 2017; Sun et al, 2016; Bellamy et al, 2006; Sarchielli et al, 2006; Juhasz et al, 2005; Petersen et al, 2005; Lassen et al, 2002; Tajti et al, 1999; Gallai et al, 1995; Goadsby et al 1990; Goadsby et al, 1988).

As of the date of approval of this protocol, erenumab 70 mg and 140 mg SC QM have been approved in the United States, European Union (EU), and other regions for the prevention of migraine in adults.

A detailed description of the chemistry, pharmacology, efficacy, and safety of erenumab is provided in the Investigator's Brochure and regional label.

3.3 Benefit/Risk Assessment

The identified risks for AMG 334 are documented in Appendix A of the currently approved IB (Edition 11: February 2020). A limited number of adverse drug reactions (injection site reactions, constipation, muscle spasm, and pruritis) have been identified at low frequencies (< 5%) in clinical trials. In post-marketing settings, hypersensitivity reactions (including rash, angioedema and anaphylactoid reactions) and constipation with serious complications have been

reported. Available safety data for the clinical trials with AMG 334 are summarized in Section 6.3 of the AMG 334 Investigator’s Brochure, Annex 2.

4. Objectives, Endpoints and Hypotheses

4.1 Objectives and Endpoints

Objectives	Endpoints
Primary	

 To evaluate the effect of erenumab compared with placebo on achieving MOH remission during the double-blind treatment period (DBTP) 	
 Absence of MOH at month 6 as defined by mean monthly acute headache medication days (AHMD) < 10 days over months 4, 5, and 6 (week 12 through 24) OR mean monthly headache days (MHD) < 14 days over months 4, 5, and 6 (week 12 through 24) of the DBTP where AHMD include any eDiary day in which an acute headache medication intake is reported
Primary Estimand	

The estimand for the primary efficacy endpoint consists of:
 
 The target population, which includes subjects diagnosed with CM and MOH who have a history of at least 1 preventive treatment failure and do not use opioid medication for more than 4 days per month The endpoint, which is the absence of MOH at month 6 as defined by mean monthly AHMD < 10 days over months 4, 5, and 6 (week 13 through 24) OR mean MHD < 14 days over months 4, 5, and 6 (week 13 through 24) of the DBTP The intercurrent event, which is adherence to treatment. The treatment effect of interest will be assessed for all randomized subjects in the target population who receive at least 1 dose of investigational product (IP), regardless of adherence to treatment. The summary measure, which is the odds ratio of absence of MOH between each erenumab dose group (ie, 70 mg or 140 mg) and the placebo group 	

Approved

Objectives	Endpoints
Secondary	

 To evaluate the effect of erenumab compared with placebo in reducing acute headache medication days (AHMD) during the DBTP 	
 Change from baseline in mean monthly AHMD over months 4, 5, and 6 (week 13 through 24) of the DBTP

The estimand for the secondary objective on AHMD consists of:
 
 The target population, which includes subjects diagnosed with CM and MOH who have a history of at least 1 preventive treatment failure and do not use opioid medication for more than 4 days per month. The endpoint, which is the change from baseline in mean monthly AHMD over months 4, 5, and 6 (week 13 through 24) of the DBTP The intercurrent event, which is adherence to treatment. The treatment effect of interest will be assessed for all randomized subjects in the target population who receive at least 1 dose of investigational product (IP) and have at least 1 change from baseline in MHD, regardless of adherence to treatment. The summary measure, which is the difference in mean of the endpoint between each erenumab dose group (ie, 70 mg and 140 mg) and the placebo group 	

 To evaluate the effect of erenumab compared with placebo on sustaining MOH remission during the DBTP 	
 Sustained MOH remission during DBTP, as defined by absence of MOH at months 3 (week 12) and 6 (week 24) of the DBTP, and “absence of MOH” is achieved when mean monthly AHMD < 10 days OR mean MHD < 14 days over the respective 3-month period

The estimand for the secondary objective on sustained absence of MOH consists of:
 
 The target population, which includes subjects diagnosed with CM and MOH who have a history of at least 1 preventive treatment failure and do not use opioid medication for more than 4 days per month The endpoint, which is the sustained MOH remission during DBTP, as defined by absence of MOH over months 1, 2, and 3 (week 1 through week 12) AND over months 4, 5, and 6 (week 13 through 24) of the DBTP. Absence of MOH is achieved when mean monthly AHMD < 10 days OR mean MHD < 14 days over the respective 3-month period The intercurrent event, which is adherence to treatment. The treatment effect of interest will be assessed for all randomized subjects in the target population who receive at least 1 dose of investigational product (IP), regardless of adherence to treatment. The summary measure, which is the odds ratio of sustained MOH remission between each erenumab dose group (ie, 70 mg and 140 mg) and the placebo group 	

 To evaluate the effect of erenumab compared with placebo on reducing the impact of migraines on physical impairment and everyday activities as measured by the Migraine 	
 Change from baseline in mean monthly average physical impairment domain scores as measured by the MPFID over months 4, 5, and 6 (week 13 through 24) of the DBTP

Approved

Objectives	Endpoints
Physical Function Impact Diary (MPFID) during the DBTP ^a	
 Change from baseline in mean monthly average impact on everyday activities domain scores as measured by the MPFID over months 4, 5, and 6 (week 13 through 24) of the DBTP

The estimand for the secondary objective on MPFID consists of:
 
 The target population, which includes subjects diagnosed with CM and MOH who have a history of at least 1 preventive treatment failure and do not use opioid medication for more than 4 days per month The endpoints, which include (1) the change from baseline in mean monthly average physical impairment domain scores and (2) the change from baseline in mean monthly average impact on everyday activities domain scores as measured by the MPFID over months 4, 5, and 6 (week 13 through 24) of the DBTP The intercurrent event, which is adherence to treatment. The treatment effect of interest will be assessed for all randomized subjects in the target population who receive at least 1 dose of investigational product (IP) and have at least 1 change from baseline in the respective domain score, regardless of adherence to treatment. The summary measure, which is the difference in mean of the endpoint between each erenumab dose group (ie, 70 mg and 140 mg) and the placebo group 	

 To evaluate the effect of erenumab compared to placebo on change from baseline in headache impact scores as measured by the Headache Impact Test (HIT-6)^a 	
 Change from baseline in mean HIT-6 score over months 4, 5, and 6 (week 13 through 24) of the DBTP

The estimand for the secondary objective on HIT-6 consists of:
 
 The target population, which includes subjects diagnosed with CM and MOH who have a history of at least 1 preventive treatment failure and do not use opioid medication for more than 4 days per month The endpoint, which is the change from baseline in mean HIT-6 total score over months 4, 5, and 6 (week 13 through 24) of the DBTP The intercurrent event, which is adherence to treatment. The treatment effect of interest will be assessed for all randomized subjects in the target population who receive at least 1 dose of investigational product (IP) and have at least 1 change from baseline in HIT-6 total score, regardless of adherence to treatment. The summary measure, which is the difference in mean of the endpoint between each erenumab dose group (ie, 70 mg and 140 mg) and the placebo group 	
Safety	

 To evaluate the safety and tolerability of erenumab in subjects with CM-MOH 	
 Adverse events Vital signs

^a In the EU region only, HIT-6 will replace MPFID as a secondary endpoint and MPFID will be evaluated as an exploratory endpoint. In non-EU regions, MPFID will remain as a secondary endpoint while HIT-6 will be evaluated as an exploratory endpoint.

Approved

Objectives	Endpoints
Exploratory (Double-blind treatment period)	

 To explore the effect of erenumab compared with placebo in promoting conversion to EM 	
 Achievement of conversion to episodic migraine (EM) at month 3 defined as mean MHD < 14 days over months 1, 2, and 3 (week 1 through 12) of the DBTP Achievement of conversion to EM at month 6, defined as mean MHD < 14 days over months 4, 5, and 6 (week 13 through 24) of the DBTP Achievement of conversion to EM over 6 months, defined as mean MHD < 14 days over months 1 through 6 (week 1 through 24) of the DBTP

 To explore the effect of erenumab compared with placebo on the change of at least moderate pain intensity MHD from baseline to the DBTP 	
 Change from baseline in MHD of at least moderate pain intensity at monthly assessment time points Change from baseline in mean at least moderate pain intensity MHD over months 4, 5, and 6 (week 13 through 24) of the DBTP Achievement of at least 30%, 50%, and 75% reductions from baseline in at least moderate pain intensity MHD at monthly assessment time points Achievement of at least 30%, 50%, and 75% reduction from baseline in mean at least moderate pain intensity MHD over months 4, 5, and 6 (week 13 through 24) of the DBTP

 To explore the effect of erenumab compared with placebo on the change from baseline in monthly migraine days (MMD) during the DBTP 	
 Change from baseline in MMD at monthly assessment time points Change from baseline in mean MMD over months 4, 5, and 6 (week 13 through 24) of the DBTP Achievement of at least a 30%, 50%, and 75% reductions from baseline in MMD at monthly assessment time points Achievement of at least 30%, 50%, and 75% reductions from baseline in MMD mean over months 4, 5, and 6 (week 13 through 24) of the DBTP

Approved

Objectives	Endpoints

 To explore the effect of erenumab compared with placebo on the change from baseline in average headache pain severity during the DBTP 	
 Change from baseline in the monthly average pain severity score of qualified headache days at monthly assessment time points Change from baseline in the mean monthly average pain severity score of qualified headache days over months 4, 5, and 6 (week 13 through 24) of the DBTP

 To explore the effect of erenumab compared with placebo on the change from baseline in migraine-free days during the DBTP 	
 Change from baseline in monthly migraine-free days at monthly assessment time points of the DBTP Change from baseline in mean monthly migraine-free days over months 4, 5, and 6 (week 13 through 24) of the DBTP

 To explore migraine-related disability metrics as measured by the migraine functional impact questionnaire (MFIQ) 	
 Change from baseline in MFIQ domain scores and overall impact on usual activities global item score at assessment time points

 To explore migraine-related disability and productivity as measured by the Migraine Disability Assessment (MIDAS) Questionnaire 	
 Change from baseline in MIDAS total score, absenteeism score and presenteeism score at assessment time points during DBTP Cumulative (sum of) changes from baseline in MIDAS total score, absenteeism score and presenteeism score over 6 months during DBTP

 To explore the effect of erenumab compared with placebo on the change from baseline in health resource utilization (HRU) 	
 Occurrence of at least 1 headache-related hospitalization or outpatient HRU during the DBTP Occurrence of at least 1 headache-related hospitalization during the DBTP Occurrence of at least 1 headache-related outpatient HRU during the DBTP Occurrence of at least 1 headache-related outpatient emergency room visit during the DBTP Occurrence of at least 1 headache-related outpatient urgent care visit during the DBTP

Approved

Objectives	Endpoints
	
 • Occurrence of at least 1 headache-related outpatient clinic visit during the DBTP

 • To explore the effect of erenumab compared with placebo on the change from baseline in depression and anxiety symptoms 	
 • Change from baseline in Generalized Anxiety Disorder 7-item scale (GAD-7) score at assessment time points • Change from baseline in Beck Depression Inventory-II (BDI-II) score at assessment time points

 • To explore the effect of erenumab compared with placebo on the change from baseline in measures of sleep quality 	
 • Change from baseline in each of the sleep questionnaire domain scores at assessment time points

 • To explore the effect of erenumab compared with placebo on the subject's assessment of the change in clinical status since the start of treatment 	
 • Change in clinical status as measured by the Patient's Global Impression of Change (PGIC) as assessed by the subject at month 6 of the DBTP

 • To explore the effect of erenumab compared to placebo on the change from baseline in allodynia symptoms 	
 • Change from baseline in Allodynia Symptoms Checklist-12 (ASC-12) score at assessment time points
Exploratory (Open-label treatment period)	

 • To explore the rate of MOH relapse in the end of open-label treatment period (OLTP) 	
 • MOH relapse at year 1, defined as both mean monthly AHMD \geq 10 days over months 11, 12, and 13 (week 41 through 52) AND mean MHD \geq 14 days over months 11, 12, and 13 (week 41 through 52) in subjects who achieved MOH remission at month 6 of the DBTP Note: This endpoint will be analyzed among subjects who were treated with erenumab throughout the entire study

 • To explore absence of MOH at end of OLTP 	
 • Absence of MOH at end of study as defined by mean monthly AHMD $<$ 10 days over months 11, 12, and 13 (week 41 through 52) OR mean MHD $<$ 14 days over months 11, 12, and 13 (week 41 through 52)

 • To explore sustainability of MOH remission during OLTP 	
 • Sustained absence of MOH over 1 year as defined by absence of MOH over the DBTP (months 1, 2, and 3 [week 1 through 12], OR months 4, 5, and 6 [week 13 through 24]) AND OLTP (months 11, 12, and 13 [week 41 through 52]).

Approved

Objectives	Endpoints
	
Note: “Absence of MOH” is achieved when mean monthly AHMD < 10 days OR mean MHD < 14 days over the respective 3-month period
 
This endpoint will be analyzed among subjects who were treated with erenumab throughout the entire study


 To explore change in AHMD, MMD, and MHD of at least moderate pain intensity 	
 Change from baseline in mean AHMD, MMD and MHD of at least moderate pain intensity at assessment time points Change from week 24 (OLTP baseline) in mean AHMD, MMD, and MHD of at least moderate pain intensity at assessment time points during OLTP

 To explore everyday activities as measured by the MPFID 	
 Change from baseline in monthly average impact on everyday activities score as measured by the MPFID at assessment time points Change from week 24 (OLTP baseline) in monthly average impact on everyday activities score as measured by the MPFID at assessment time points during OLTP

 To explore physical impairment as measured by the MPFID 	
 Change from baseline in monthly average physical impairment score as measured by the MPFID at assessment time points Change from week 24 (OLTP baseline) in monthly average physical impairment score as measured by the MPFID at assessment time points during OLTP

 To explore the daily activity impact of headache as measured by the HIT-6 	
 Change from baseline in HIT-6 total score at week 52 Change from week 24 (OLTP baseline) in HIT-6 total score at week 52

 To explore migraine-related disability metrics as measured by MFIQ 	
 Change from baseline in MFIQ domain scores and overall impact on usual activities global item score at week 52 Change from week 24 (OLTP baseline) in MFIQ domain scores and overall impact on usual activities global item score at week 52

Approved

Objectives	Endpoints

 To explore migraine-related disability and productivity as measured by the MIDAS Questionnaire 	
 Change from baseline in MIDAS total score, absenteeism score and presenteeism score at week 52 Change from week 24 (OLTP baseline) in MIDAS total score, absenteeism score, and presenteeism score at week 52
Exploratory (Opioid-treated Cohort Only)^a	

 To explore the effect of erenumab compared with placebo in reducing consumption of opioids in subjects stratified to the opioid-treated cohort during DBTP 	
 Change from baseline in monthly opioid/opioid-containing medication days at assessment time points during DBTP Change from baseline in mean monthly opioid/opioid-containing medication days over months 4, 5, and 6 (week 13 through 24) of the DBTP

 To explore the effect of erenumab compared with placebo in reducing consumption of opioids in subjects stratified to the opioid-treated cohort during OLTP 	
 Change from baseline in monthly opioid/opioid-containing medication days at assessment time points during OLTP

^a In addition to these objectives/endpoints, all primary, secondary, and exploratory objectives and endpoints will be evaluated for the opioid-treated cohort.

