4.2 Hypotheses

The primary clinical hypothesis of Study 20170703 is that preventive treatment with monthly injections of erenumab is superior to placebo in achieving MOH remission for subjects with CM-MOH in the nonopioid-treated cohort who have a history of at least 1 preventive treatment failure as measured by the absence of the MOH status based on the mean over months 4, 5, and 6 (**week 13 through 24**) of the DBTP.

The secondary clinical hypotheses of Study 20170703 are that preventive treatment with monthly injections of erenumab is superior to placebo in reducing AHMDs over months 4 to 6 (**week 13 through 24**) of the DBTP; sustaining MOH remission during the entire DBTP; reducing migraine-related impact on physical functioning and everyday activities as measured by Migraine Physical Function Impact Diary (MPFID) physical function and everyday activities domains (non-EU) or migraine-related impact on physical functioning as measured by the Headache Impact Test 6 (HIT-6) (EU only).

For subjects with CM-MOH allocated to the opioid-treated cohort, an additional exploratory clinical hypothesis of Study 20170703 is that preventive treatment with

Approved

monthly injections of erenumab could help reduce opioid use as measured by the mean change in monthly opioid medication days from baseline over months 4, 5, and 6 (**week 13 through 24**) of the DBTP. Formal statistical testing does not apply to this exploratory clinical hypothesis.

5. Study Design

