5.1 Overall Design

Study 20170703 is a phase 4, randomized, double-blind, double-dummy, parallel-group, placebo-controlled study to evaluate the safety and efficacy of erenumab against placebo in a CM population with MOH and prior history of treatment failure. Subjects will be enrolled based on fulfilment of the International Classification of Headache Disorders, 3rd Edition (ICHD-3) CM and MOH criteria and will not be advised to early discontinue acute medication. During randomization, subjects will be separated into 2 distinct cohorts based on their opioid medication use at baseline. Subjects with an opioid medication use > 4 days per month during the baseline period will be allocated to the opioid-treated cohort. Subjects with an opioid medication use of ≤ 4 days per month during the baseline period will be allocated to the nonopioid-treated cohort. The randomization process on the nonopioid-treated cohort will be balanced based on the following stratum:

- Concomitant oral migraine preventive treatment initiated before screening and taken during baseline (Yes or No).

Subjects allocated to the opioid-treated cohort will be analyzed separately as an exploratory cohort.

Subjects who successfully complete the 24-week DBTP of the study will be offered an opportunity to continue in an OLTP of 28-weeks duration. Subjects who received erenumab treatment during the DBTP will continue to receive the same erenumab dose during the OLTP. Subjects who received placebo during the DBTP will be allocated in a 1:1 ratio to receive either erenumab 70 mg or 140 mg SC QM during the OLTP. All subjects will remain blinded to their original DBTP treatment assignment.

The overall study design is described by a study schema in [Section 2.1](#). The endpoints are defined in [Section 4.1](#).

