 - ≥ 10 days of triptans, ergots, OR
 - ≥ 15 days of NSAIDs or simple analgesics intake
109. At least 2 acute headache medication days per week for each week with at least 5 diary days
110. Demonstrated at least 80% compliance with the eDiary (eg, must complete eDiary items on at least 23 out of 28 days during the baseline period)

Approved

6.4 Exclusion Criteria Part 2

Approved

Study procedures

224. Likely to not be able or available to complete all protocol required study visits or procedures, and/or comply with all required study procedures (eg independent completion of eDiary items) to the best of the subject's and investigator's knowledge

Approved

Concomitant treatment at baseline

- 242.** Taken a **short-acting** opioid or opioid-containing analgesic for any indication for > 15 days during baseline period
- 243.** **Short-acting** opioid use during baseline period that in the opinion of the investigator or Amgen's physician, if consulted, constitutes any of the following:
- misuse (use that is contrary to the prescriber's directions, eg, unsolicited dose escalation)
 - abuse (use for nonmedical intention, eg, euphoria or altered consciousness)
 - dependence (use that is compulsive or potentially harmful)
 - diversion (transfer of a legally prescribed controlled substance from the individual for whom it was prescribed to another person for any illicit use)
227. Changed or planning to change the dose of an allowed concomitant medication that may have migraine preventive effect during baseline period or postrandomization
228. Use of any of the excluded concomitant medications, procedures or devices as outlined in [Section 7.1.7](#).

Approved

Medical conditions newly diagnosed during baseline

- 229. Unstable or clinically significant medical condition that, in the opinion of the investigator or Amgen physician, if consulted, would pose a risk to subject safety or interfere with the study evaluation, procedures or completion
- 244.** At risk of self-harm or harm to others as evidenced by scoring ≥ 1 point in BDI-II item 9 (**Suicidal Thoughts or Wishes**) and concomitant demonstration of strong suicidal ideation (ie, presence of suicidal planning)
- 231. Evidence of drug or alcohol abuse or dependence or "recreational use" of illicit drugs as demonstrated by subject self-report, medical records or a positive drug screen test at baseline

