7.2 Method of Treatment Assignment

Subjects will be randomized in a 1:1:1 allocation ratio, to erenumab 70 mg/mL SC every 4 weeks, erenumab 140 mg/mL SC every 4 weeks, or matching placebo, respectively, in a double-blind manner for nonopioid-treated cohort and opioid-treated cohort separately.

Approved

The randomization will be performed by **IRT**, and the randomization number will be assigned by **IRT** and appear on the **IRT** randomization document. The randomization number is different than the subject identification number and will not be utilized by the site as a subject identifier.

The randomization will be stratified by concomitant treatment with an oral preventive (Yes or No) in the nonopioid-treated cohort.

The randomization date is to be documented in the subject's medical record and on the enrollment CRF.

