10.4.2 Methods of Analyses

10.4.2.1 General Considerations

Formal statistical analyses using statistical models and hypothesis testing will be performed for the nonopioid-treated cohort only.

Summary statistics will be computed by treatment group and visit. For continuous endpoints, the following descriptive statistics will be computed: number of observations, means, medians, standard deviations, standard errors, first and third quartiles, minimums and maximums, and 2-sided 95% CIs of the means (CIs will be provided for efficacy endpoints only). For categorical endpoints, the summaries will contain the number and percentage of subjects in each category.

The dichotomous efficacy endpoints will be analyzed using the stratified Cochran-Mantel-Haenszel (CMH) test after the missing data is imputed as nonresponse. Continuous secondary endpoints will be analyzed using a linear mixed effects model including treatment group, baseline value, stratification factor, scheduled visit, and the interaction of treatment group with scheduled visit, without any imputation for missing data at the monthly level.

The 2 erenumab dose groups will be compared with placebo for the primary and secondary efficacy endpoints in the nonopioid-treated cohort using a simple fixed sequence procedure with study-wise type I error rate $\alpha = 0.05$. The order of the endpoints to be tested is prespecified below. If any test is not significant at the $\alpha = 0.05$ level, then no further testing will be performed.

Primary and secondary endpoints in erenumab 140 mg versus placebo:

1. Absence of MOH at month 6 (**week 24**) of DBTP (140 mg)
2. Change from baseline in mean monthly AHMD over months 4, 5, and 6 (**week 13 through 24**) of the DBTP (140 mg)
3. Sustained MOH remission during DBTP (140 mg)

Primary and secondary endpoints in erenumab 70 mg versus placebo:

4. Absence of MOH at month 6 (**week 24**) of the DBTP (70 mg)
5. Change from baseline in mean monthly AHMD over months 4, 5, and 6 (**week 13 through 24**) of the DBTP (70 mg)
6. Sustained MOH remission during DBTP (70 mg)

Patient reported outcome-related secondary endpoints for the non-EU region

7. Change from the baseline in mean monthly average physical impairment domain scores as measured by the MPFID over months 4, 5, and 6 (**week 13 through 24**) of the DBTP (140 mg)

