9.1 General Considerations

Formal statistical analyses using statistical models and hypothesis testing will be performed for the nonopioid-treated cohort only. Descriptive statistics will be produced for the opioid-treated cohort. **The classification of cohorts (opioid-treated and nonopioid-treated) used for the primary analysis will be based on the cohort value determined at randomization. As sensitivity analysis, the primary endpoint, secondary endpoints, and change from baseline in mean monthly opioid/opioid-containing medication days will be summarized descriptively for the 'observed' opioid-treated subjects who reported >4 days of opioid medication use in the eDiary data during the last 28 days of baseline period.**

Summary statistics will be computed by treatment group and visit. For continuous endpoints, the following descriptive statistics will be computed: number of observations, means, medians, standard deviations, standard errors, first and third quartiles, minimums and maximums, and 2-sided 95% CIs of the means (CIs will be provided for efficacy endpoints only). For categorical endpoints, the summaries will contain the number and percentage of subjects in each category.

The dichotomous efficacy endpoints will be analyzed using the stratified Cochran-Mantel-Haenszel (CMH) test after the missing data is imputed as nonresponse. Continuous secondary endpoints will be analyzed using a linear mixed effects model including treatment group, baseline value, stratification factor, scheduled visit, and the interaction of treatment group with scheduled visit, without any imputation for missing data at the monthly level. **In case more than 10% subjects had stratification error within non-opioid treated cohort (ie. stratified incorrectly between the with vs. without concomitant oral migraine preventive medication strata), sensitivity analysis will be conducted for the model-based analysis for primary and secondary endpoints, using the ‘observed’ concomitant oral migraine preventive medication reported by site as strata in CMH tests.**

The 2 erenumab dose groups will be compared with placebo for the primary and secondary efficacy endpoints in the nonopioid-treated cohort using a simple fixed sequence procedure with study-wise type I error rate $\alpha = 0.05$. The order of the endpoints to be tested is prespecified below. If any test is not significant at the $\alpha = 0.05$ level, then no further testing will be performed.

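### The opioid-cohort objective is a comparison with placebo, but the plan specifies only by-arm descriptive statistics there and no erenumab-minus-placebo difference or confidence interval

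*Protocol*

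**What the plan says.** **Objective and endpoint.** Protocol 4.1 (repeated in SAP 2.1) sets the objective for this cohort in the double-blind period: "To explore the effect of erenumab compared with placebo in reducing consumption of opioids in subjects stratified to the opioid-treated cohort during DBTP". One of its two endpoints is "Change from baseline in mean monthly opioid/opioid-containing medication days over months 4, 5, and 6 (week 13 through 24) of the DBTP"; the other is the same change at each monthly time point. The protocol synopsis (Overall Design) also describes the cohort as evaluated against placebo, in an exploratory way.

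**Hypothesis.** In Protocol 4.2 the primary and secondary hypotheses claim superiority over placebo. The opioid hypothesis says that erenumab could help reduce opioid use, "as measured by the mean change in monthly opioid medication days from baseline over months 4, 5, and 6". It names no comparator, and the same section exempts it from formal testing.

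**Who is in the cohort.** Protocol 5.1: "Subjects with an opioid medication use > 4 days per month during the baseline period will be allocated to the opioid-treated cohort". Protocol 6.4 (criterion 242) excludes anyone who took a short-acting "opioid or opioid-containing analgesic for any indication for > 15 days during baseline period".

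**Randomization.** Protocol 7.2: "Subjects will be randomized in a 1:1:1 allocation ratio", done separately and double-blind in each cohort. Stratification by oral preventive use is specified only for the nonopioid cohort. Protocol 10.1 plans up to 46 subjects per arm.

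**Analysis.** Protocol 10.4.2.1: "Formal statistical analyses using statistical models and hypothesis testing will be performed for the nonopioid-treated cohort only". SAP 9.1 repeats this and adds: "Descriptive statistics will be produced for the opioid-treated cohort". The statistics listed are per arm and visit, with a 95% CI of each mean. SAP 9.1 also plans a sensitivity summary of subjects observed to be opioid-treated, which is descriptive too.

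**General exploratory rules.** Protocol 10.4.2.2 calls for differences from placebo with 95% CIs and p-values. SAP 9.5.3 applies the primary and secondary methods to exploratory endpoints. Neither rule says which cohort it covers.

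**The concern.** The objective asks for a contrast, and the statistics named for this cohort are three separate arm means. A contrast is the only summary that uses the randomization of up to 138 subjects.

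The wording of 4.2 adds to the difficulty. The statistic that most directly matches it is one erenumab arm's mean change with that arm's own interval. The cohort is selected on the quantity that is later analyzed as the endpoint, so some fall in every arm is expected without any drug effect, on top of any placebo response. Someone who reads an erenumab arm alone could take that fall for efficacy. The number that would guard against this is not among the planned outputs.

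**Working it through.** **1. Is there a planned figure to reproduce?** Not for this cohort: the documents give no power, SD or precision for opioid days. The only power statement, in Protocol 10.1, concerns the nonopioid primary endpoint. It reproduces with 183 × 0.8 = 146.4 per arm (85.9% for 70 mg, above 99.9% for 140 mg) and is not in question here.

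**2. Do the general exploratory rules supply the contrast?** Not as written.
- Protocol 10.4.2.2 would bring a model and p-values into this cohort, against 10.4.2.1 and 4.2.
- The model in SAP 9.5.2, and the ANCOVA in 9.5.3 for endpoints with one or two post-baseline time points, both include the stratification factor. Protocol 7.2 defines that factor only for the nonopioid cohort.
- The covariates in Protocol 10.2.2 and SAP 4.1 are likewise set for the nonopioid cohort.

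No text says which rule prevails.

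**3. How large can a within-arm fall be with no drug effect?** The documents give no distribution of opioid days, so this is a simulation over assumed values.
- Each subject has a constant daily probability p of opioid use, drawn from a beta distribution with mean m/28 and intraclass correlation ρ: a = (m/28)(1/ρ − 1), b = (1 − m/28)(1/ρ − 1).
- Baseline days ~ Binomial(28, p). Post-baseline monthly mean = Binomial(84, p)/3, for months 4 to 6.
- Subjects with 5 to 15 baseline days are kept (Protocol 5.1 and 6.4). Change = post-baseline minus baseline.
- 3,000,000 subjects were simulated per setting. Two arms of 46 were then drawn 4,000 times from those selected.

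| Mean m (days per 28) | ρ | Mean change | SD of change | One arm's 95% CI wholly below 0 | Mean difference between arms | Between-arm 95% CI excludes 0 |
|---|---|---|---|---|---|---|
| 3 | 0.1 | −1.065 | 2.32 | 85.5% | 0.002 | 4.6% |
| 3 | 0.2 | −0.644 | 2.52 | 39.8% | 0.002 | 4.6% |
| 3 | 0.4 | −0.304 | 2.65 | 12.9% | 0.002 | 5.1% |
| 5 | 0.1 | −0.720 | 2.44 | 49.7% | 0.001 | 5.1% |
| 5 | 0.2 | −0.450 | 2.57 | 21.8% | −0.002 | 4.7% |
| 5 | 0.4 | −0.208 | 2.68 | 7.9% | 0.001 | 4.7% |
| 8 | 0.1 | −0.241 | 2.59 | 9.4% | −0.006 | 5.7% |
| 8 | 0.2 | −0.150 | 2.65 | 6.5% | −0.006 | 5.0% |
| 8 | 0.4 | −0.064 | 2.71 | 3.8% | −0.009 | 5.1% |

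The shift runs from negligible to about one day. The 15-day ceiling limits it, because subjects with high counts are also removed. The difference between arms is zero apart from simulation error, and its interval errs at the nominal 5% rate.

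**4. How precise would the contrast be?** Half-width = 1.96 × SD × √(2/n), with n = 46 as planned, or 46 × 0.8 ≈ 37 if the 20% dropout assumed for the nonopioid cohort also applied here. The SDs are assumed.

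| SD of change | n = 46 | n = 37 |
|---|---|---|
| 2.4 | 0.98 | 1.09 |
| 3 | 1.23 | 1.37 |
| 4 | 1.63 | 1.82 |
| 5 | 2.04 | 2.28 |
| 6 | 2.45 | 2.73 |

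**The case against.** A reader might infer more: that regression to the mean will pass for a drug effect in this trial. The documents do not support that. Baseline opioid days are counted before randomization, the cohort has its own concurrent blinded placebo arm, and that arm is tabulated beside the two erenumab arms. Selection moves all three alike. Nor does any passage treat a within-arm interval below zero as evidence of efficacy, so the 4% to 86% in the table describes a misreading, not a planned inference.

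Other points on the sponsor's side also carry weight:
- The descriptive analysis is a deliberate choice, stated consistently. The 138 is a cap set for feasibility (Protocol 5.2), with no power claim, and the cohort serves other endpoints too.
- An unadjusted difference and its interval need neither a model nor a test, and can be worked out from the planned means and standard errors. It would therefore be wrong to say that the plan forbids the contrast.
- The synopsis supplies the comparator that 4.2 leaves out.
- The companion open-label objective in Protocol 4.1 also asks for a comparison with placebo, at a time when placebo subjects have moved to erenumab. That is arguably the harder problem, but a separate one.

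What remains is this. A difference that a reader must work out is neither prespecified nor adjusted for baseline, and with at most 46 per arm chance imbalance in baseline opioid days matters. The two sets of rules still disagree about this cohort.

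**Conclusion.** The point holds as a mismatch between objective and analysis. The plan asks a placebo-controlled question of a randomized, blinded cohort and does not specify the estimate that answers it. The general exploratory rules do not fill the gap, because they name no cohort and depend on a factor defined for the other one.

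The risk of misreading is conditional: it arises only if an erenumab arm is read without its placebo arm. In that case the fall from selection alone would be about 0.06 to 1.07 days. That range assumes a population mean of 3 to 8 opioid days per 28, an intraclass correlation of 0.1 to 0.4, binomial day-to-day variation and no dropout. It is not an estimate for this trial, and it is not a bias in the between-arm comparison. The sponsor should make the change, but the primary and secondary conclusions do not depend on it.

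**What to change.** 1. In SAP 9.1 and 9.5.3, for the double-blind opioid-day endpoints in the opioid-treated cohort, report each erenumab dose minus placebo with a 95% CI, adjusted for baseline opioid days. Use ANCOVA on the month 4 to 6 mean, or the planned mixed model without the stratification factor. Label it descriptive and give no p-value.
2. Make this an explicit exception to the sentence that limits models to the nonopioid cohort, and state whether Protocol 10.4.2.2 and SAP 9.5.3 otherwise apply to the opioid cohort. Record the change in SAP Section 10.
3. In the opioid hypothesis (Protocol 4.2, SAP 2.2), name placebo as the comparator, and note that a within-arm change is not in itself evidence of effect.

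The cost is some wording and one table from data already collected, settled before this cohort is unblinded. It stays within the commitment not to test. The drawback is precision: the half-width is about 1.0 to 2.7 days under the assumptions above, and the interval may be uninformative if the cohort recruits poorly. Baseline adjustment may narrow it, by an amount that the documents do not allow one to predict. If the sponsor wants no model at all in this cohort, an unadjusted difference with its CI would still answer the objective, but without protection against chance baseline imbalance.
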